11.0 Provisions to Monitor the Data to Ensure the Safety of Subjects*

Vitamin D and L-cysteine is a common micronutrients and is widely present in many food items, such as milk, cheese, eggs and green vegetables. The dose used falls within normal range for a healthy person consuming a healthy diet. Thus, this research is considered and falls under minimal risk. The Data Safety Monitoring Plan committee will review clinical laboratory reports for any unanticipated observation. Names of members of DSMP committee are enclosed. DSMP will meet once in three months or as required in case any adverse side effect is reported by any subject or seen in clinical report.

12.0 Withdrawal of Subjects*

Subjects found to be consuming over the counter supplement, positive pregnancy tests or not able to follow the instructions will be withdrawn from the study. Any data collected on subject withdrawn from the study will not be used in any analyses. The investigator will ask a subject who is withdrawing whether the subject wishes to provide further data collection from routine medical care.

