5.0 Multi-Site Research* N/A (This is only site)

6.0 Study Timelines*

Potential subjects will be contacted over phone or potential subjects may call in response to advertisement and agrees to participate in this study will be asked to come to the clinic after fasting overnight. Fasting blood will be collected after written informed consent. Blood collected at V₋₁ will serve as the sample for the screening visit for the clinical trial. Subjects meeting the inclusion/ exclusion criteria will continue in the clinical trial. All subjects will fill out the complete standard health history before the study and at each visit during the study. This clinical trial will be registered at the ClinTrial.gov site.

Initially, all of the study subjects will be provided placebo supplementation as a placebo run-in period for one month before randomization. Visit 2 (V₀) is for obtaining baseline levels after the run-in period. AA-subjects will be block randomized into four groups. Members of the groups will ingest capsules containing placebo and supplements, orally, daily: (I) placebo (P); (II) LC (1000 mg); (III) VD (2000 IU); (IV) VD and LC. Each capsule will contain a placebo or cholecalciferol (2000 IU) or LC (1000 mg). Placebo group will take two placebo capsules a day in the morning; II LC group will receive two capsules of LC daily; (III) VD group will take two capsules and each capsule will contain 1000 IU VD daily; (IV) VD+LC group will take daily two capsule containing 1000 IU+500 mg LC. Supplements will be taken daily with food at breakfast for 6 months, while participants continue to carry on a normal lifestyle. During the placebo run-in period, all subjects will also take two placebo capsules daily. Based on previous experience, we expect a dropout rate of about 16% as a result of non-compliance, lost contact, taking another medicine, or a subject found to have another disorder. We expect that at least 30 subjects in each group will complete the study. Overnight fasting blood will be collected at each visit. Also, anthropomorphic data, body weight, and height (BMI), the record of any drug use, any adverse effects/complaints (related or unrelated), and Questionnaire will be collected at each visit by the nurse. It is likely to require ~90 minutes to collect the subject's history and other data in interviews with the nurse/dietician and investigators.

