The placebo run-in period is meant to stabilize subjects in the study and will prevent any effect due solely to inclusion in the study. Placebo and supplement capsules will be similar in appearance, taste, texture, and smell, and will be provided by the [name]/pharmacist, who will have the codes for which subjects are assigned to which supplement or placebo. Both subjects and investigators will be blinded to the supplement each subject will receive. [name] will randomize the subjects. Documentation about capsules/supplements to be used is enclosed on last page (page 9) of this protocol.

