7.0 Study Endpoints*

PROTOCOL TITLE: Optimization of 25(OH) vitamin D levels in African Americans

Primary Endpoints: Blood levels of 25(OH)VD, TNF- α , and HOMA-IR.

Safety Endpoints: Serum calcium (Ca²⁺), PTH, liver, and kidney function tests will be carried out at visits 0, 2, 4, and 6. Whole blood CBC and pregnancy tests will be done at all visits.

Secondary Endpoints: Blood levels of 1,25(OH)₂VD, HbA_{1c}, and pro-inflammatory and anti-inflammatory cytokines (such as IL-2, IL-6, and IL-10).

We will also perform tests to monitor liver and kidney function tests at each visit and complete blood count analyses for any sign of any anemia or unexpected changes in white or red blood cell profiles.

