10.0 Data Management* and Confidentiality

Analyses of data will be performed by the biostatistician, [name]. A *p*-value of less than 0.05 for a statistical test will be considered significant. Data will be analyzed statistically to compare the 4 groups at baseline and various visits using ANOVA. The Wilcoxon signed-rank or paired *t*-test will be used to determine significant changes after supplementation for each treatment group, and the ANOVA test to compare the 4 treatment groups on changes. The results for the pairwise comparisons among the 4 time points will determine whether there is a significant change in the outcome variables over time. The effect of covariates or possible confounders (age, sex, BMI, initial levels of outcomes, etc.) will be controlled for and tested for their significant effects by including them in the repeated measures model used.

Based on animal studies, co-supplementation with LC+VD will be more successful and raise serum 25(OH)VD levels by nearly 30 ng/mL(17, 18). Our goal is to raise circulating 25(OH)VD levels by an average of 30 ng/mL, and reduce IR levels by 35% in all AA subjects receiving combined VD+LC supplementation. To observe a significant response or change, a sample size of 7 for 25(OH)VD, and 27 for IR were considered adequate using a paired *t*-test conducted at 5% level of significance and 80% power. We chose a goal of 30 subjects in each group who complete the study in the VD+LC supplementation and other groups. Based on our experience from a previously completed clinical trial (H-09-073), enrollment of and consent from 160 AA volunteers who participate in blood collection for screening should give us more than the required sample size of 30 subjects in each group (120 in 4 groups) after factoring in a dropout rate of about 16% for screen failures, withdrawal before randomization, or those who did not complete all the visits. Our experience also suggests that nearly 190 subjects will need to be contacted to achieve our goal of 160 AA volunteers who complete the written consent form and are enrolled in this clinical trial. This takes into account the fact that only about 85% of those initially contacted will indeed show up for the screening visit and complete the written informed consent.

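### Section 12.0 bars all data on withdrawn subjects from every analysis, so randomized subjects withdrawn during the 6 treatment months leave the group comparison and the final safety summaries with every visit they completed

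*Protocol*

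**What the plan says.** Section 12.0 gives three grounds for withdrawal: use of an over-the-counter supplement, a positive pregnancy test, and being "not able to follow the instructions will be withdrawn from the study". It then rules: "Any data collected on subject withdrawn from the study will not be used in any analyses". The next sentence has the investigator ask a withdrawing subject about further data from routine care.

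Section 6.0 places randomization after a one-month placebo run-in, followed by 6 months of supplements. The events behind the three grounds are looked for throughout. Section 7.0 says "Whole blood CBC and pregnancy tests will be done at all visits", and section 6.0 says "the record of any drug use, any adverse effects/complaints (related or unrelated), and Questionnaire will be collected at each visit by the nurse". Section 6.0 also expects "a dropout rate of about 16% as a result of non-compliance, lost contact, taking another medicine", among other reasons.

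Section 10.0 compares the groups at baseline and at the visits, uses "the ANOVA test to compare the 4 treatment groups on changes", and refers to four time points and a repeated measures model. It defines no analysis set of all randomized subjects. For safety, section 7.0 lists serum calcium together with "PTH, liver, and kidney function tests will be carried out at visits 0, 2, 4, and 6".

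**The concern.** Randomization makes the four arms comparable as randomized. Removing subjects for something that happened afterwards keeps that protection only if removal is unrelated to arm or to outcome, and the rule does nothing to secure this. The contrast at stake is VD+LC against VD alone for 25(OH)VD, TNF-α and HOMA-IR.

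Two further losses do not depend on bias. Measurements properly taken before withdrawal are thrown away. And subjects who took assigned capsules and had calcium, PTH, liver and kidney tests are missing from the final account of safety, which then describes only those who were not withdrawn.

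This is not a matter left to an analysis plan that is not at hand. The protocol fixes the rule itself, and a plan that kept these data would contradict it.

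**Working it through.** **1. Does the rule reach randomized subjects?** The sentence has no time limit. Its three grounds can all occur during the 6 months of supplementation, and the checks that would reveal them (pregnancy tests, drug-use record, questionnaire) are made at each visit. No other section exempts randomized subjects, earlier visits or safety data. So it does reach them. For subjects withdrawn during screening or run-in, exclusion causes no bias between arms.

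**2. What is discarded per subject?** Visits 0, 2, 4 and 6 (section 7.0) are read as the four time points of section 10.0, with 0 as the post-run-in baseline.

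| Withdrawn | Time points already collected | Discarded |
|---|---|---|
| after visit 2, before visit 4 | 0, 2 | 2 of 4 |
| after visit 4, before visit 6 | 0, 2, 4 | 3 of 4 |
| at visit 6 (e.g. positive pregnancy test) | 0, 2, 4, 6 | 4 of 4 |

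A repeated measures model that accepts incomplete subjects could use all of these.

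**3. How many subjects?** The plan's own figure reproduces: 160 × (1 − 0.16) = 134.4, or 134.4 / 4 = 33.6 per group, above the 30 required. The loss is 160 × 0.16 = 25.6. But section 6.0 attributes the 16% to non-compliance, lost contact, other medicines and other disorders, while section 10.0 attributes it to screen failures, withdrawal before randomization and incomplete visits. Neither gives the share withdrawn after randomization on section 12.0's grounds. That number lies between 0 and about 26 and cannot be narrowed. Nor does the text say whether the ban covers subjects lost to contact.

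**4. Can a bias be sized, and would keeping the data remove it?** Only under assumptions. Suppose 8% of one arm is lost, being the lowest 8% on a latent score correlated r = 0.5 with the final change, and loss in the other arms is random. The shift in that arm's mean is r·φ(z)/(1 − p) = 0.5 × 0.1487 / 0.92 = 0.081 SD. If withdrawal unrelated to arm and outcome is assumed instead, the shift is 0.

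Keeping data up to withdrawal does not supply the missing final visit. If an earlier change correlates ρ with the final change, the remaining shift is roughly 0.081 × (1 − ρ²): at ρ = 0.5, 0.081 × 0.75 = 0.06 SD; at ρ = 0.7, 0.081 × 0.51 = 0.04 SD. With baseline data only, ρ = 0 for the change and nothing is removed. Such a shift therefore comes partly from withdrawal itself and only partly from the data ban.

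**The case against.** The strongest reply is that the bias is unproven and would not be cured by retaining data. Section 6.0 says "Both subjects and investigators will be blinded to the supplement each subject will receive", which makes arm-dependent withdrawal less likely, and nothing in the document shows that it would occur. A subject withdrawn before visit 6 has no visit-6 value under either wording. All of this stands. A reader might infer that the rule inflates the type I error by a stated amount. The document does not support that: the number withdrawn and its relation to arm and outcome are both unknown, and step 4 shows that the amended wording would remove only part of any such effect.

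A reader might also infer that the rule hides toxicity. That is not supported either. None of the three grounds is an adverse event or an abnormal laboratory value, and the committee's review of laboratory reports during the trial (section 11.0) is unaffected. What remains is narrower: these subjects are absent from the final safety summaries.

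A third reply is that this is a mechanistic trial (section 2.0), for which a complier-focused question is reasonable, and that keeping all visits would include some made while a subject was taking undisclosed vitamin D, which acts directly on a primary endpoint. This is a fair point about how the data are used, and a sensitivity analysis answers it. It does not justify deleting visits made before the supplement use began, or any visit of a subject withdrawn for another reason.

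**Conclusion.** The point holds on the wording alone. Followed as written, section 12.0 removes randomized subjects on post-randomization grounds, discards 2, 3 or 4 of 4 time points for those withdrawn after visit 2, after visit 4 or at visit 6, and leaves them out of the final safety summaries. The loss of data is certain for each such subject, and only their number is unknown. It rests on one reading, that visits 0, 2, 4 and 6 are the four analysis time points.

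Bias in VD+LC versus VD is possible if withdrawal differs by arm and relates to outcome. Its size and direction cannot be derived, blinding makes it less likely, and the fix would remove it only in part. The case for change is the departure from the randomized set and the needless loss of valid data. It does not depend on a quantified error rate. The defect is modest but clear, and should be corrected before analysis, because deciding later whose data to keep could be influenced by the results.

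**What to change.** Replace the sentence in section 12.0 with:

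> All randomized subjects are analysed in the arm to which they were randomized, using all outcome data collected up to withdrawal in the repeated measures model. Safety data are summarised for everyone who took study capsules. A sensitivity analysis is limited to compliant subjects and leaves out visits made while a subject was taking a non-study supplement.

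Since everyone takes placebo during the run-in, make clear that study capsules here means those assigned at randomization. Reconcile the new text with the next sentence of section 12.0: it asks withdrawing subjects about further data that the present ban would leave unused, so state whether and how such data will be analysed.

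The withdrawal grounds do not change. The cost is a wording amendment and slightly more data handling, with no extra subjects or visits. The estimated effect may be somewhat smaller than in compliers alone, which is why the compliant-subject analysis is kept alongside.

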8.0 Procedures Involved*

Fasting blood will be drawn after an overnight fast into pre-cooled tubes kept in an ice bucket: 2 mL in a tube without anticoagulant (for the chemistry profile), 1 mL each EDTA-blood for HbA_{1c} and 1 mL for CBC, 8 mL for isolation of plasma, and 12 mL for PBMC isolation. Samples will be transported in an ice-bucket. EDTA-blood will be centrifuged, and the clear plasma saved in several aliquots for various assays. The plasma will be stored at -80°C. Information on age, height, body weight and records of any medication use will be collected from each patient at the time of enrollment. HbA_{1c}, CBC, and blood chemistry profile for glucose, Ca⁺⁺, liver, and kidney function tests, and pregnancy tests will be done at the clinical chemistry labs of LSUHSC-Shreveport. Frozen aliquots stored at -80°C will be used for all assays. Appropriate control and standards will be used, and analyses will be done in duplicate for each sample. This will eliminate inter-assay variability.

PBMC isolation and PCR studies: PBMC will be isolated using Histopaque (Sigma-Aldrich catalog # 10771) from EDTA -blood as described in our previous publications. We will assay GSH and VD metabolism genes in PBMC as described in our earlier studies.

25(OH)VD and 1,25(OH)₂VD assays: We have already standardized tests for simultaneous determinations of total 25(OH)VD and 1,25(OH)₂VD in human plasma using UPLC-MS/MS.

Whole blood total GSH, L-cysteine, will be determined using HPLC, and a whole blood Glucose-6-Phosphate Dehydrogenase (G6PD) Activity Assay Kit (Sigma, Cat # MAK015); TNF- α will be determined using an ELISA kit from R&D Systems (Minneapolis, MN). Insulin will be determined using ELISA kits from ALPCO Diagnostics (Salem, NH), and the HOMA insulin resistance index will be calculated (136). IL-2, IL-6, and IL-10 will be determined using ELISA kits from R&D Systems (Minneapolis, MN). All appropriate controls and standards as specified by the manufacturer's kits will be used; control samples will be analyzed each time to check the variation from plate to plate on different days to reduce the variability of assays. All of the analyses will be done in duplicate on each sample.

Total 24 mL blood will be collected (2 mL in a tube without anticoagulant (for the chemistry profile), 1 mL each EDTA-blood for HbA_{1c} and 1 mL for CBC, 8 mL for isolation of plasma, and 12 mL for PBMC isolation).

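### Section 12.0 offers randomized subjects who go off protocol only routine-care follow-up, which does not yield the three primary endpoints, so subjects who could still attend have no final outcome

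*Protocol*

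**What the plan says.** Section 12.0 of the protocol names three triggers: use of over-the-counter supplements, a positive pregnancy test, and failure to follow instructions. On the last it says that subjects "not able to follow the instructions will be withdrawn from the study". Two further rules follow. On data: "Any data collected on subject withdrawn from the study will not be used in any analyses". On follow-up: "The investigator will ask a subject who is withdrawing whether the subject wishes to provide further data collection from routine medical care". No section describes a subject who is off capsules and still attends study visits.

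Section 7.0 gives the primary endpoints: "Blood levels of 25(OH)VD, TNF- α , and HOMA-IR". Section 8.0 says how they are obtained. Vitamin D metabolites come from "simultaneous determinations of total 25(OH)VD and 1,25(OH)₂VD in human plasma using UPLC-MS/MS", TNF-α from a research ELISA, and HOMA-IR from a study insulin ELISA. On the material it adds: "Frozen aliquots stored at -80°C will be used for all assays". Section 6.0 has fasting blood drawn at each visit, and Section 7.0 numbers the visits 0, 2, 4 and 6.

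On losses, Section 6.0 says "we expect a dropout rate of about 16% as a result of non-compliance, lost contact, taking another medicine", or another disorder being found. Section 10.0 uses the same 16% but describes it as covering failed screening, departure before randomization and incomplete visits.

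**The concern.** The trial's hypothesis compares VD+LC with VD alone, and Section 10.0 compares the four groups on change by ANOVA. A subject with no later study draw has no end-of-study change. If adherence or use of other products differs between arms, comparing those who remain is no longer a comparison of the randomized groups.

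At stake is whether the trial can estimate the effect of being assigned one regimen rather than another. An analysis plan can choose how to handle missing values, but it cannot restore values that were never collected. Follow-up after going off protocol is a rule of conduct, and this protocol fixes it.

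**Working it through.** **1. Can routine care supply the endpoints?** Setting Sections 7.0 and 8.0 against the follow-up sentence in 12.0:

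- 25(OH)VD: the study uses its own UPLC-MS/MS method on stored plasma. Routine care might occasionally give a value from another assay, which is not interchangeable without a bridging step that the protocol does not describe.
- TNF-α: a research ELISA, not something to expect in the ordinary care of people whom Section 15.0 describes as healthy adults.
- HOMA-IR: needs insulin from the study ELISA together with glucose, both fasting. Routine care may give a glucose value, but not the study insulin.

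None of the three is available as this trial measures it. In addition, the bar on using any withdrawn subject's data in Section 12.0 would keep whatever routine care did supply out of every analysis.

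**2. Who is affected?** The link runs through the withdrawal triggers. A subject who takes a supplement or does not follow instructions is removed from the study, not only from the capsules. Such a person has not necessarily refused further visits. Of the four causes listed in Section 6.0, three (non-compliance, another medicine, another disorder) do not in themselves prevent attendance. Loss of contact does.

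**3. The plan's own figure.** Inputs: 160 enrolled (Section 4.0), 16% loss (Sections 6.0 and 10.0), four groups, 30 completers per group (Section 10.0).

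- Completers: 160 × (1 − 0.16) = 134.4, or 134.4 / 4 = 33.6 per group. This exceeds 30, so the plan's statement is reproduced.
- Losses: 160 × 0.16 = 25.6, or 25.6 / 4 = 6.4 per group.

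The number of completers is therefore not the problem.

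**4. Can the bias be sized?** Let R be the mean change among retained subjects in an arm, L the mean change that lost subjects would have shown, and p the share of randomized subjects lost. The arm mean over all randomized is (1 − p)R + pL, so the retained-only mean is off by p(R − L). For two arms with the same p:

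bias in the contrast = p × [(R₁ − R₀) − (L₁ − L₀)]

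If p differs by arm, it is p₁(R₁ − L₁) − p₀(R₀ − L₀). With equal loss, bias is zero when the arm contrast among lost subjects equals that among retained subjects. It equals p times the retained contrast when lost subjects show no contrast.

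Neither factor is in the documents:

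- If the overall 16% holds, p lies between 0 (all loss before randomization) and 16% (all loss after it). Nothing places it within that range.
- The difference in contrasts is unknown, and it stays unknown when those subjects are not drawn.

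**The case against.** The strongest reply is that the follow-up sentence speaks of someone who is leaving, and for such a person an optional request for routine-care data is reasonable. Stopping capsules is not itself a listed trigger. That is correct, and it limits the point to subjects withdrawn under the listed triggers, together with the absence of any route for attending off capsules. It does not remove the point, because the instruction-following trigger turns non-adherence into full withdrawal.

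A second reply is that Section 2.0 describes a mechanistic focus and leaves a full efficacy trial for later, so response while taking the supplement is a coherent target. It is. But an on-treatment analysis remains possible when everyone is followed, while the randomized comparison cannot be recovered when they are not.

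A third reply is that the bar on using withdrawn subjects' data already produces the same restriction. This stands in part: each rule alone leaves the final outcome out of the analysis, so both must change.

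A reader might infer several stronger things that the documents do not support:

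- **A bias of a stated number of SDs, or a stated gain in precision from keeping 40 per group.** This treats all 16% (or the 25% by which 120 falls short of 160) as loss after randomization. Section 10.0 counts people never randomized within the 16%, and the 25% is slack in the target, not an expected loss.
- **That most expected losses are retrievable.** Three of four named causes is not a majority of subjects, because no counts are given.
- **That safety laboratory information ends at withdrawal.** Calcium, liver and kidney tests are ordinary clinical chemistry, which routine care could supply.

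**Conclusion.** The point holds as a correctable weakness in conduct. As written, Section 12.0 leaves randomized subjects who go off protocol but could still attend without any final primary outcome, and limits the four-group comparison to those not withdrawn. The target of 30 completers per group survives. What is exposed is the interpretation of the comparison as a randomized one.

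The direction and size of any bias cannot be stated from the documents. The conclusion rests on two assumptions: that routine care of healthy adults will not produce these study assays, and that at least some withdrawn subjects would still agree to be drawn. The documents contradict neither.

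**What to change.** In Section 12.0:

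1. Define two statuses: off study capsules or off protocol, and withdrew consent for further visits or lost to contact.
2. Ask randomized subjects in the first status who still consent to attend the remaining scheduled fasting draws, at least V6, with the same assays and visit payment.
3. Record the date of and reason for going off capsules or off protocol.
4. Amend the sentence barring use of withdrawn subjects' data so that these values enter the randomized comparison, with an on-treatment analysis as a supplement. Without this step the extra draws would go unused.

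The rules on when capsules are stopped need not change. Whether draws continue after a positive pregnancy test or a newly found disorder should be left to the investigator and the IRB.

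The cost is protocol and consent wording. The visits, assays and \$50 payments are already planned for every enrolled subject. The drawbacks are that some subjects will decline and that off-capsule values dilute the on-treatment effect, which the supplementary analysis can show separately.
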